### 3.6 Exploratory Assessment

The exploratory endpoints explore the influence of LBP-EC01 on the urinary tract microbiota. These will be summarized based by treatment on the ITT Population and Evaluable Population.

#### 3.6.1 *Urine Culture and Sensitivity*

Urine culture and sensitivity assessments will be made at the timepoints specified in the SoA of the protocol. Incidence and summaries of CFU/mL levels of all non-*E. coli* bacteria isolated will be presented at each scheduled visit. Overall summaries of all bacteria (including *E. coli*) may also be presented. All data will be listed.

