#### 2.1.3 *Exploratory Objectives*

To explore the influence of LBP-EC01 on the urinary tract microbiota.

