### 2.3.3 Exploratory Endpoints

The exploratory endpoints involve exploring the effects of LBP-EC01 on the urinary tract microbiota. These include:

- Urine culture and sensitivity (persistent, recurrent *E. coli*, new colonizing new infections will be documented)
- Evaluation of bacterial biomarkers (e.g., phage sensitivity/resistance, bacterial antibiotic resistance, bacterial metagenomic analysis)

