## 3 STATISTICAL METHODOLOGY

### 3.1 General Considerations

#### 3.1.1 *Definition of Baseline*

Baseline is defined as the last measurement prior to the first dose of study drug unless otherwise specified.

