### 3.5 Pharmacodynamic Assessment

The secondary endpoints concern the pharmacodynamics of LBP-EC01. These will be summarized by treatment based on the PD Population.

*E. coli* assessments will be made at the timepoints specified in the SoA of the protocol. Incidence of the following endpoints will also be summarized with counts and percentages of patients at Day 1 (Baseline), Day 2, Day 3, Day 5, Day 7 (EOT), Day 14 and Day 28:

- Reduction in urinary *E. coli* burden at timepoint from Baseline
- Biological elimination of *E. coli* at timepoint after Baseline. Biological elimination is defined as measurement below  $1 \times 10^3$  CFU/mL

The following *E. coli* parameters will be derived based on all available post-Baseline data and summarized and listed:

- Time to 1 log reduction in urinary *E. coli* from Baseline
- Biological elimination at any timepoint.
- Incidence and time to recurrence of *E. coli* colonization. Recurrence is defined as past biological elimination followed by increase above the patient's baseline CFU/mL.
- Incidence of infection based on clinical signs and symptoms defined as an adverse event marked as a UTI symptom and followed by antibiotic use.

*E. coli* parameters will be summarized first for the total CFU/mL in a patient (sum of CFU/mL for all *E. coli* strains) but may also be summarized by strain specific *E. coli* colonization (individual strain CFU/mL per patient).

All *E. coli* assessment data will be listed.

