#### 3.6.3 *Microbiological Isolates*

Any persisting microbiological isolates identified will have all related data listed, including bacteriophage host range and antibiotic resistance patterns. Genetic sequencing of isolates will be included in the separate metagenomics analysis.

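### The exploratory urine-culture endpoint names new colonisers, but SAP 3.6.1 plans only by-visit summaries of non-*E. coli* bacteria, with no comparison to each patient's baseline culture

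*SAP*

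**What the plan says.** The exploratory objective (SAP 2.1.3) concerns the effect of LBP-EC01 "on the urinary tract microbiota". Section 2.3.3 turns this into two endpoints. The first is "Urine culture and sensitivity (persistent, recurrent *E. coli*, new colonizing new infections will be documented". The punctuation is loose, but the natural reading is four things to record: persistent *E. coli*, recurrent *E. coli*, new colonisers and new infections.

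Section 3.6.1 is the analysis section for that endpoint, in the ITT and Evaluable Populations. It commits to one summary: "Incidence and summaries of CFU/mL levels of all non-*E. coli* bacteria isolated will be presented at each scheduled visit". It then adds "Overall summaries of all bacteria (including *E. coli*) may also be presented. All data will be listed".

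Related text stands elsewhere:
- Section 3.5 summarises *E. coli* elimination by timepoint and overall, and the incidence of infection (a UTI-symptom adverse event followed by antibiotic use). It also covers recurrence: "Recurrence is defined as past biological elimination followed by increase above the patient's baseline CFU/mL".
- Section 3.6.3 provides a listing: "Any persisting microbiological isolates identified will have all related data listed, including bacteriophage host range and antibiotic resistance patterns".
- Sections 3.6.2.3 and 3.6.3 send metagenomics and sequencing of isolates to a separate plan.
- Section 3.1.1 supplies a reference point: "Baseline is defined as the last measurement prior to the first dose of study drug unless otherwise specified".

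**The concern.** An organism is new only in relation to what the patient carried before dosing. Section 3.6.1 defines no such comparison. Its incidence is the share of patients with an organism at a visit, which is a point prevalence. A patient who carried the same second organism before dosing and at every visit is counted exactly like a patient in whom it first appeared after treatment.

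Patients with catheters or asymptomatic bacteriuria may well carry other organisms at entry. For an agent aimed at *E. coli*, organisms that appear once treatment has started are a central part of any effect on the microbiota. If the planned table looks flat over time or similar between arms, it could be taken as evidence that no new colonisation occurred, which it cannot show.

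**Working it through.** The SAP gives no figure on this point, so there is none to reproduce. The check is whether the planned table determines the number of new acquirers.

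**Inputs.** Section 2.2.4 gives 36 patients at 2:1, that is 36 × 2/3 = 24 on LBP-EC01 and 36 × 1/3 = 12 on placebo. The SAP gives no carriage figures, so those below are assumptions. Every patient is taken to be cultured at both visits.

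**Formula.** For one species in an arm of n patients, let a carry it at baseline and b at a later visit, and let x of the b be new. The other b − x were carriers at baseline, so b − x ≤ a, which gives x ≥ b − a. New acquirers come from the n − a patients free at baseline, so x ≤ n − a, and also x ≤ b. Hence max(0, b − a) ≤ x ≤ min(b, n − a).

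**Results.**
- n = 24, a = 12, b = 12: x from max(0, 0) = 0 to min(12, 12) = 12.
- n = 24, a = 6, b = 12: x from 6 to min(12, 18) = 12.
- n = 24, a = 10, b = 10: x from 0 to min(10, 14) = 10. The table reads 10/24 = 42% at both visits in every case.
- n = 12, a = 6, b = 6: x from 0 to 6.
- n = 24, a = 0, b = 6: x = 6 exactly.

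The by-visit counts fix x only in special cases, such as zero carriage at baseline.

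**Between arms.** Combine the first and fourth lines. Both arms read 50% at both visits, yet the data could be 12 new acquirers among the 12 treated patients free at baseline and 0 among the 6 such placebo patients. The placebo arm does not remove the ambiguity.

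**By species or pooled.** Section 3.6.1 does not say which. In a by-species table, replacement of one species by another shows as one row falling and another rising; only turnover within a species cancels. In a single any-organism row, a later carrier may have a new species whether or not another species was present before, so the upper limit rises to b. With n = 24, a = b = 18, the range is 0 to 6 for one species but 0 to 18 patients with some new species in the pooled row.

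**Other sections.** Section 3.5 concerns *E. coli*, and its infection item identifies no organism. Section 3.6.3 lists persisting isolates without defining the term. None tabulates newly acquired non-*E. coli* organisms.

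**The case against.** The strongest reply is that most of the endpoint is covered. Recurrent *E. coli* is defined and summarised in section 3.5. Persistent *E. coli* can be read there as the complement of elimination. Symptomatic infection has its own definition. Persisting isolates are listed. All of this stands, so a reader who infers that the whole endpoint lacks an analysis goes too far.

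A reader might also infer that the microbiota objective goes unanswered, or that replacement by another *E. coli* strain is missed. The document does not support either conclusion. Metagenomics and sequencing belong to a separate plan that is not at hand, and section 3.5 allows strain-level summaries as an option.

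Nor does the table merely count: it also summarises CFU/mL and may be by species, in which case replacement between species would be visible.

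Finally, section 2.3.3 says only that "new colonizing new infections will be documented", and section 3.6.1 lists all data. With 36 patients, each organism can be followed through the listings. It is therefore wrong to say that new colonisation cannot be found at all. But the tracing would be done without a prespecified rule, and treatment assignments are unblinded before the analysis is generated (section 5.2).

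The endpoint is exploratory and nothing is tested (section 3.1.5), which limits the consequence but does not supply the missing definition.

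**Conclusion.** The point holds in a limited form. New colonisers are a named part of the endpoint, and the SAP contains no baseline-referenced definition or summary of them for non-*E. coli* organisms. The planned by-visit table leaves the number of new acquirers anywhere between max(0, b − a) and min(b, n − a) for a given species. That range can be wide, as with 0 to 12 of 24 in the illustration. Its width in this trial depends on baseline carriage, which the SAP does not give; the lack of identification itself needs only some carriage at baseline together with room for both gain and loss. Descriptive reading of one exploratory endpoint is affected, and no primary or secondary result.

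**What to change.** In section 3.6.1, classify each non-*E. coli* species per patient against the baseline culture as defined in section 3.1.1:
- new: not isolated at baseline, isolated at a later visit at or above a stated CFU/mL threshold, so that a single low-count isolate does not qualify by default;
- persistent: isolated at baseline and later;
- cleared: isolated at baseline and not later, with the visits that count stated.

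Present by treatment the number and percentage of patients with at least one new species, at any post-baseline visit and by visit. The denominator is patients with a baseline culture and at least one post-baseline culture. For a given species, use patients free of it at baseline. The choice matters and should be written down. For example, if 10 of 24 carry a species at baseline and 5 others gain it, the species rate is 5/(24 − 10) = 5/14 = 36%. If those 5 are the only patients with any new species, the patient-level rate is 5/24 = 21%.

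Keep the by-visit table as support, and state whether it is by species and whether it shows baseline. Leave *E. coli* elimination and recurrence under the section 3.5 definitions, with no second definition of recurrence here.

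The cost is SAP wording, a derived classification from cultures already planned, and one or two extra exploratory tables. The rule should be fixed before unblinding.

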#### 3.6.2 *Bacterial Biomarkers*

Bacterial biomarkers will be collected at the timepoints specified in the SoA of the protocol.

##### 3.6.2.1 *Phage Sensitivity/Resistance*

Phage sensitivity and resistance by *E. coli* isolates will be collected at the timepoints specified in the SoA of the protocol. Incidence of the following will be summarized by isolate for the cocktail and each individual phage:

- Isolates that yield ennumerable plaques (PFU/mL)
- Isolates that yield ennumerable plaques (PFU/mL) or that demonstrate “lysis from without”
- Insensitive isolates (no ennumerable plaques or no “lysis from without”)

All phage sensitivity and resistance will be listed by patient for each *E. coli* isolate, including *E. coli* sensitivity to the cocktail and to each individual phage.

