### 3.2.6 *Subgroup Analyses*

Subgroup analyses of these Analysis populations may also be performed. Such subgroups include, but are not limited to:

- Patients with indwelling catheterizations and patients with intermittent catheterizations
- Patients with *E. coli* sensitive to LBP-EC01 and patients with *E. coli* insensitive to LBP-EC01

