##### 3.6.2.2 *Bacterial Antibiotic Resistance*

Patient incidence of antibiotic resistance will be summarized across all *E. coli* isolates. All patient antibiotic resistance data will be listed, including MIC values and interpretations.

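### Phage sensitivity is summarized only by isolate, so the percentage depends on who clears E. coli and the table need not report emergent insensitivity

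*SAP*

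**What the plan says.** Section 3.6.2.1 covers sensitivity of E. coli isolates to the phage cocktail and its components. Collection is repeated: "Phage sensitivity and resistance by *E. coli* isolates will be collected at the timepoints specified in the SoA of the protocol". The summary rule is "Incidence of the following will be summarized by isolate for the cocktail and each individual phage", with three isolate categories based on plaques and lysis from without. The patient appears only in a listing: "All phage sensitivity and resistance will be listed by patient for each *E. coli* isolate". Section 3.6.3 adds a listing of all data on persisting isolates.

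The surrounding text settles points that this subsection leaves open:
- Section 3.6, on all exploratory endpoints: "These will be summarized based by treatment on the ITT Population and Evaluable Population".
- Section 3.6.1, on organisms other than E. coli: "bacteria isolated will be presented at each scheduled visit".
- Section 3.6.2.2: "Patient incidence of antibiotic resistance will be summarized across all *E. coli* isolates".

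Section 3.2.6 names patients with sensitive and with insensitive E. coli as a possible subgroup ("Subgroup analyses of these Analysis populations may also be performed"). It does not say which isolate or timepoint classifies a patient.

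**The concern.** With the isolate as unit, a patient's weight in the percentage is the number of isolates that patient supplies, and this is partly a result of treatment. If the drug removes sensitive strains and leaves insensitive ones, the sensitive isolates drop out of the denominator and the percentage insensitive rises, although no strain has changed. Shown by treatment, this could be read as resistance induced by the drug.

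The table also has no line for a patient who was sensitive at baseline and insensitive later. One percentage can arise from insensitivity present at the start or from insensitivity that developed on treatment.

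The subgroup in Section 3.2.6 rests on the same results. If a later isolate may classify a patient, the subgroup is conditioned on something that happened after treatment began.

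**Working it through.** The SAP gives no isolate count or expected percentage for this summary, so there is no figure to reproduce. The check is illustrative.

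**Inputs from the SAP**
- 36 patients randomized 2:1 (Section 2.2.1): 36 × 2/3 = 24 on LBP-EC01 and 36 × 1/3 = 12 on placebo.
- Seven E. coli timepoints, baseline plus six (Section 3.5). These stand in for the isolate schedule, which the SAP leaves to the protocol.

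**Assumptions**
- One isolate per culture-positive visit. Section 3.5 allows several strains per patient, so the real number may be higher.
- Isolates are counted over all visits.

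**1. Weight of persistently colonised patients.** Let P of the 24 active patients stay positive at all 7 visits, and let the others be positive at c visits. The persisters' share of isolates is 7P / (7P + (24 − P)c).

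| P | Share of patients | c = 3 | c = 2 | c = 1 |
|---|---|---|---|---|
| 4 | 16.7% | 31.8% | 41.2% | 58.3% |
| 6 | 25.0% | 43.8% | 53.8% | 70.0% |
| 8 | 33.3% | 53.8% | 63.6% | 77.8% |
| 12 | 50.0% | 70.0% | 77.8% | 87.5% |

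For example, P = 6 and c = 1 gives 42 / (42 + 18) = 70.0%. With c = 7 (nobody clears) the two shares are equal, e.g. 42 / 168 = 25.0%.

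**2. Arms differ without emergence.** Let one-sixth of each arm be insensitive at baseline (4 of 24 and 2 of 12) and positive at all 7 visits. No strain changes and nobody on placebo clears.
- Active, all 20 sensitive patients clear after baseline: 4 × 7 / (20 × 1 + 28) = 28/48 = 58%.
- Active, 10 of the 20 clear: 28 / (10 × 1 + 10 × 7 + 28) = 28/108 = 26%.
- Active, none clear: 28 / (24 × 7) = 28/168 = 17%.
- Placebo: 2 × 7 / (12 × 7) = 14/84 = 17%.
- By patient: 4/24 and 2/12, 17% in both arms in every case.

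A split by visit alone does not remove this. In the first case each post-baseline visit would show 4/4 = 100% of active isolates insensitive, against 2/12 = 17% on placebo.

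**3. Same percentage, different emergence.** Take 6 persisters (42 isolates) and 18 patients who clear after baseline (18 isolates), 60 in all.
- A: 3 persisters insensitive throughout, no emergence: 3 × 7 / 60 = 21/60 = 35%.
- B: none insensitive at baseline, all 6 persisters become so, 3 of them with 4 insensitive isolates and 3 with 3: (12 + 9) / 60 = 21/60 = 35%.
- By patient, A has 3/24 (12.5%) insensitive at baseline and 0/24 emergent; B has 0/24 at baseline and 6/24 (25%) emergent.

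**The case against.** The strongest case on the other side has five parts.

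- **Pooling over visits is not written.** A reader might infer that isolates from all visits are combined. Section 3.6.2.1 is silent on this, and Section 8 leaves detail to separate programming specifications. This stands: pooling is one reading that the silence permits. It does not remove the concern, because a by-visit layout still has an outcome-dependent denominator and no patient count.
- **Emergence can be read from the listings.** This stands. A reader might conclude that emergent resistance would be invisible, but with 36 patients the by-patient, by-isolate listings would show it. What is missing is a defined count.
- **An isolate percentage is not a biased patient percentage.** It is a different quantity, and it misleads only if taken as a patient rate or as a treatment effect. This stands, but a display by treatment invites that second use.
- **Section 3.6.2.2 is no model.** It counts patients, but across all isolates, so it too can mix baseline with later results. This stands: the contrast supports the patient as unit, not the handling of time.
- **The subgroup is optional.** This stands too. Section 3.2.6 does not say that post-treatment isolates will be used; it leaves the matter open.

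**Conclusion.** The concern holds in limited form. The isolate is the only stated unit, with no time split and no patient count. The by-isolate percentage can therefore differ between arms without any emergence, and the summary as written need not report emergent insensitivity.

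The size cannot be fixed from the SAP. In the assumed case the active arm ranges from 17% (nobody clears, no distortion) to 58% (all sensitive patients clear), against 17% on placebo. Those figures assume seven timepoints, one isolate per positive visit, counting over all visits, and insensitivity concentrated in patients who stay colonised. If insensitivity were equally common in patients who clear and patients who do not, the isolate and patient percentages would agree. A reader might also infer that persistently colonised patients must dominate the table. They are over-weighted whenever others clear, but they form the majority of isolates in only part of the range examined (31.8% to 87.5%).

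Severity is low: the endpoint is exploratory, no hypothesis is tested and the individual data are listed.

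**What to change.** In Section 3.6.2.1, add one table by treatment, for the cocktail and each phage, that counts:
- patients with at least one insensitive isolate at baseline;
- patients whose baseline isolates were all sensitive and who have at least one insensitive isolate post-baseline (emergent insensitivity).

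State the denominator, and show beside it the number of patients with any post-baseline isolate, since a patient without one cannot be seen to change. The at-least-one and all-sensitive wording also settles repeat isolates and multiple strains.

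Keep the by-isolate table as supportive and present it by visit. In Section 3.2.6, state that if the sensitive/insensitive subgroup is analysed, patients are classified from baseline isolates only.

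The cost is one extra table and one definition. The results are already to be listed by patient and isolate, so no new data are needed. Both should be fixed before unblinding.

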#### 2.2.3 *Study Drug*

LBP-EC01 is a clear to opalescent, colorless to slightly yellow, aqueous solution. LBP-EC01 is a mixture of 3 crPhages internally named as p0031-8, p00ex-2, p004k-5, which are derived from wild-type myoviridae phages that target *E. coli*. These phages have been engineered to contain

an identical CRISPR-Cas3 construct and have been combined in equal amounts at  $1 \times 10^6$  –  $1 \times 10^{12}$  PFU/mL (equivalent to approximately  $1.5 \times 10^7$  –  $1.5 \times 10^{13}$  PFU/vial). One vial of LBP-EC01 containing approximately 15 mL of solution will be steriley mixed with 45 mL of Lactated Ringer's solution (injection, USP) by the site pharmacy prior to each dose administered (details will be included in the pharmacy manual). LBP-EC01 and placebo solutions will be indistinguishable.

LBP-EC01 will be administered by bladder instillation via a newly placed urinary catheter BID at the maximum feasible dose, based on the manufacturing process (approximately  $1.5 \times 10^7$  –  $1.5 \times 10^{13}$  PFU/vial), totaling approximately 60 mL of solution via sterile catheter tipped syringe (details will be included in the pharmacy manual). The urinary catheter will be clamped and the solution left in situ for a minimum of 30 minutes (to a maximum of 40 minutes) following instillation and then it will be placed on free drainage (duration of clamp should be documented).

LBP-EC01 will be provided in a 20 mL vial containing approximately 15 mL of the crPhage cocktail. This vial will be brought to room temperature prior to mixing with 45 mL of Lactated Ringer's solution (injection, USP) under sterile conditions and placed into a sterile syringe with a catheter tip. Handling and mixing of the vials making up LBP-EC01 will be done by the unblinded study pharmacist (details are provided in the pharmacy manual). Placebo solution Lactated Ringer's solution (injection, USP) will be brought to room temperature and will also be prepared by the pharmacist under aseptic technique and placed into a sterile catheter tipped syringe. The unblinded pharmacist will use the IVRS system to determine the randomization allocation.

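### The bracketed rule for insensitive isolates joins the two absences with 'or' instead of 'and', so an isolate showing exactly one sign of phage activity is counted both as responding and as insensitive

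*SAP*

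**What the plan says.** SAP section 3.6.2.1 sets out how phage sensitivity is to be tabulated: "Incidence of the following will be summarized by isolate for the cocktail and each individual phage". Three lines follow.

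- Line 1: "Isolates that yield ennumerable plaques (PFU/mL").
- Line 2: "Isolates that yield ennumerable plaques (PFU/mL) or that demonstrate" lysis from without.
- Line 3: "Insensitive isolates (no ennumerable plaques or no" lysis from without).

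Section 2.2.3 fixes the number of components: "LBP-EC01 is a mixture of 3 crPhages internally named as" three listed codes. Section 2.3.3 names the bacterial biomarkers as an exploratory endpoint and gives as examples "phage sensitivity/resistance, bacterial antibiotic resistance, bacterial metagenomic analysis".

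The only other use of the term is in section 3.2.6, where an optional subgroup pair sets patients with E. coli "sensitive to LBP-EC01 and patients with *E. coli* insensitive to LBP-EC01" against each other. That section does not say how a patient is assigned to either side.

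**The concern.** Line 2 counts isolates that show at least one of two signs. Line 3 carries the label for isolates that do not respond and negates the same two signs, so a reader expects lines 2 and 3 to divide the isolates between them. They do not. Negating 'plaques or lysis' gives 'no plaques **and** no lysis'. The SAP writes 'no plaques **or** no lysis', and the repeated 'no' makes this a union of two absences.

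Taken literally, an isolate that forms countable plaques, the very response that line 1 records, is also insensitive unless it shows lysis from without as well. The tabulated incidence of insensitivity would then be too high, for the cocktail and for each phage, and the table would contradict itself, with lines 2 and 3 exceeding the number of isolates tested. A reader using the table to judge how much of the E. coli lay outside the product's host range would be misled.

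**Working it through.** The SAP states no figure on this point, so there is none to reproduce. The check is logical, followed by the algebra of the counts.

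**Inputs (section 3.6.2.1).** P = enumerable plaques present; L = lysis from without present. Line 1 = P. Line 2 = P or L. Line 3 as written = (not P) or (not L). Line 3 as presumably intended = (not P) and (not L).

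**Step 1: the four possible outcomes**

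| P | L | Line 1 | Line 2 | Line 3 as written | Line 3 with 'and' |
|---|---|---|---|---|---|
| yes | yes | yes | yes | no | no |
| yes | no | yes | yes | **yes** | no |
| no | yes | no | yes | **yes** | no |
| no | no | no | no | yes | yes |

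Two of the four outcomes, those with exactly one sign, sit on line 2 and on line 3 as written. With 'and', no outcome sits on both and every outcome sits on one. The nesting of line 1 within line 2 is clear from the wording and is not an error.

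**Step 2: the counts.** Let N = isolates tested, a = line 1 count, b = line 2 count, c = isolates with both signs, where 0 ≤ c ≤ a.

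- Plaques only = a − c; lysis only = b − a; neither = N − b.
- Intended insensitive count = N − b.
- Count as written = (a − c) + (b − a) + (N − b) = N − c.
- Overcount = (N − c) − (N − b) = b − c, so at least b − a (when c = a) and at most b (when c = 0).
- Lines 2 and 3 as written sum to b + (N − c) = N + (b − c) instead of N.

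**Step 3: the range.** The SAP does not give c, nor say whether both signs can be recorded for one isolate. If every responding isolate shows both signs (c = b), the written rule returns the true share q = (N − b)/N. If none does (c = 0), it returns 100%. A true 20% could thus appear as anything from 20% to 100%, and a true 50% as anything from 50% to 100%.

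**Step 4: illustration with assumed counts.** Take N = 100, a = 60 and b = 70, so that 30 isolates show neither sign. Only c varies.

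| Both (c) | Plaques only | Lysis only | Neither | Line 3 as written (N − c) | Line 3 with 'and' (N − b) | Lines 2 + 3 as written |
|---|---|---|---|---|---|---|
| 60 | 0 | 10 | 30 | 40 | 30 | 110 |
| 10 | 50 | 10 | 30 | 90 | 30 | 160 |
| 0 | 60 | 10 | 30 | 100 | 30 | 170 |

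Lines 1 and 2 are identical in all three rows (60 and 70), and the true insensitive count is 30 throughout. The count as written runs from 40 to 100, so it is driven by c, which is not a measure of insensitivity.

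**Step 5: how often the rule is used.** One cocktail plus 3 individual phages = 4 summaries.

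**The case against.** The strongest reply is that everyone will know what is meant. The label says insensitive, the line above supplies the two signs, and in ordinary prose 'no A or no B' in a bracket is commonly meant as 'neither'. The literal reading has a plaque-forming isolate called insensitive, which contradicts the label. Detailed programming specifications are a separate document under section 8, and section 5.2 provides for review of pre-final tables, where an implausibly high insensitive count would stand out. The summary is exploratory and descriptive in a study with no formal hypothesis. All isolate results are listed, and the right count can be recovered as isolates tested minus line 2. The optional subgroup in section 3.2.6 is not tied to this rule.

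Most of this stands as a limit on the consequence. It is probably a slip, it is likely to be noticed if the one-sign isolates are numerous, and the primary and secondary endpoints do not use the class. The size of the error is also unknown, and the lower end of the range is no error at all. None of it corrects the text, however. Programming specifications that have not been seen, and a later review of tables, cannot be relied on to overrule the one definition the SAP gives. An overcount from a few one-sign isolates would be less conspicuous than the extreme case. The subgroup, being optional and unlinked, adds no weight to the point.

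**Conclusion.** The definition is wrong as written. Followed exactly, it overstates the insensitive count by b − c, the number of isolates showing exactly one sign, whenever there are any such isolates. How large that is cannot be computed from the SAP: the reported share lies between the true share and 100%, depending on how often both signs are recorded together. The counts of 100 isolates used above are assumptions for illustration only.

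The reach is limited to an exploratory, descriptive tabulation. Lines 1 and 2 and the isolate listings are unaffected. The wording should be corrected, because it is an operative derivation rule for a named exploratory endpoint and because section 1 has the SAP final before database lock and requires later deviations to be documented in the study report.

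**What to change.** In section 3.6.2.1, replace 'or' with 'and' inside the bracket of the third line, so that an isolate is insensitive only if it shows neither plaques nor lysis from without. Add the check that line 2 plus line 3 equals the number of isolates tested, run separately for the cocktail and for each of the 3 phages. If the optional sensitive/insensitive subgroup in section 3.2.6 is run using this class, it should use the corrected definition.

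The cost is one word in the SAP and a matching line in the derivation. Data collection and all other analyses stay as they are.
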